2. STUDY DESIGN

The study is designed as a prospective, randomized (two-cohort) double-blinded clinical evaluation and will be conducted at multiple centers throughout the United States. Approximately 500 patients will be included and followed for a period of 2 years. Clinical Assessments will be performed at baseline, 6 weeks, 6 months, 1 and 2 years after surgery.

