7. PATIENT SELECTION

Enrollment: Approximately 500 patients will be enrolled and followed for a period of 24 months in order to assess patient outcomes. Each center is expected to enroll approximately 100 patients (50 in each group). The investigator is responsible for evaluating each patient against the following criteria and assuring that the patient meets the following requirements in order to be enrolled in the study. Each patient must meet all the inclusion criteria and none of the exclusion criteria to be considered for enrollment.

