- Radiographic evaluation via Mediolateral and anteroposterior x-rays as is standard of care. The prevalence and location of radiolucency and/or osteolysis is evaluated on both AP and lateral views at each patient’s routine postoperative

follow-up visits. These evaluations are performed by each patient's operating surgeon.

- Complications, adverse events, and survivorship data will be collected and reported. This information will be gathered at each of the study follow-up visits.

c. Data Collection Periods:

Data will be collected pre-operatively, intra-operatively, and post-operatively at 6 weeks, 6 months, and 1 year. All time point windows are determined using the date of surgery (DOS) as day 0, including all annual visits. The visit windows are as follows:

Pre-operative: within 3 months prior to the date of the surgery excluding

*Pre-operative radiographs. Pre-operative radiographs taken within 12 months of scheduled knee replacement surgery are sufficient.

Intra-operative: within 2 weeks after the date of surgery

6 weeks: DOS + 6 weeks ± 4 weeks

6 months: DOS + 6 months ± 45 days

1 year: DOS + 1 year ± 90 days

2 year: DOS + 2 year ± 90 days

Table 1. Schedule of study assessments

Data Collected	Pre-op Baseline	Operative Discharge	6 Weeks	6 Months	1 Year	2 Years
Obtain Written Informed Consent	X					
Demographics	X					
Intra Operative		X				
EQ-5D	X		X	X	X	X
New-KSS	X		X	X	X	X
FJS			X	X	X	X
Knee Pain Evaluation Form				X	X	X
Radiographic Alignment	X		X	X	X	X
Adverse Event Reporting (When Present)		(X)	(X)	(X)	(X)	(X)

10. Analysis to be Performed on Data (e.g. Statistical Analysis)

Analysis of the data will be performed using SPSS version 21. Comparative Statistics will be run between outcomes data stratified by both groups: Analysis of variance (AVOVA) will be used to assess the difference between each group, with post-hoc t-tests to demonstrate significance. Separate analyses will be performed to evaluate power of sample sizes and any correlative affect that demographic/clinical variables may have on patient outcomes.

11. Monitoring of data collection

The Sponsor will monitor all data collected for accuracy and completion. The site will be monitored at least once per calendar year following the initial/first-monitoring visit.

12. Patient Identification

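### Section 10 does not say how scores measured four or five times per patient, or missed visits, enter its ANOVA, and no plausible reading uses the data both validly and fully

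*Combined protocol and SAP*

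**What the plan says.** Section 2 (Study Design) sets the visit schedule: "Clinical Assessments will be performed at baseline, 6 weeks, 6 months, 1 and 2 years after surgery". It also gives the size and length of the trial: "Approximately 500 patients will be included and followed for a period of 2 years". Section 5 splits the patients into 250 per group.

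Table 1 in Section 9 lists EQ-5D and the new KSS at baseline and all four post-operative visits, so five times. FJS is listed at the four post-operative visits only, and the Knee Pain Evaluation Form at three. The opening sentence of Section 9c stops at 1 year, but the visit windows ("2 year: DOS + 2 year ± 90 days") and Table 1 include 2 years.

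Section 10 is the only analysis text supplied. It says that "Comparative Statistics will be run between outcomes data stratified by both groups", and then names the method: "Analysis of variance (AVOVA) will be used to assess the difference between each group, with post-hoc t-tests to demonstrate significance". It names no patient effect, visit factor, covariance structure, comparison visit, baseline adjustment or missing-data rule.

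Section 7.3 ends follow-up for patients whose implant is removed or revised, or whose sensor malfunctions during surgery. Some incomplete series are therefore built into the design.

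**The concern.** Scores from one patient at successive visits are correlated, and some patients will miss visits. A method described only as a between-group ANOVA does not address either fact.

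The reference to post-hoc tests adds to the doubt. With two groups, one-way ANOVA and the two-sample t-test are the same test (F equals t squared), so a post-hoc test has nothing left to separate. The sentence makes more sense if a factor with more levels, such as visit, is in the ANOVA. The text does not say so, and it does not say whether the patient would enter as well.

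The study hypothesis in Section 3 rests on pain, return to activities and satisfaction, and these repeated scores carry much of it. The choice among readings affects the error rate, the number of patients analysed and the 2-year comparison. As written, it could be made after the data are seen.

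**Working it through.** The plan gives no alpha, power, effect size, correlation or loss rate, so there is no figure of its own to reproduce. From the documents: 250 patients per group, four post-operative visits and five measurements including baseline. Assumed for illustration: two-sided alpha 0.05, within-patient correlation ρ of 0.3 to 0.7 (equal between all visits), 5-10% missing at each visit, or 10-20% missing at 2 years.

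**Reading 1: four post-operative visits pooled, no patient term.** The variance of the overall group difference is understated by the factor 1 + (4 − 1)ρ. The true error rate is 2 × (1 − Φ(1.96/√factor)).
- ρ = 0.3: factor 1.9, SE ratio √1.9 = 1.38, error 15.5%.
- ρ = 0.5: factor 2.5, SE ratio 1.58, error 21.5%.
- ρ = 0.7: factor 3.1, SE ratio 1.76, error 26.6%.

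A simulation of 8,000 trials per setting, with a group-by-visit ANOVA and no patient term, gave 16.2%, 22.2% and 26.1%. These rates concern the overall group effect.

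**Reading 2: repeated-measures ANOVA with listwise deletion.** This has a within-patient term, but keeps only patients with every visit. If misses are independent, the share kept over four visits is (1 − q)^4.
- q = 5%: 0.95^4 = 0.815, about 407 of 500 kept, 18.5% dropped.
- q = 10%: 0.90^4 = 0.656, about 328 of 500 kept, 34.4% dropped.

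With baseline as a fifth measurement, the shares kept are 77.4% and 59.0%.

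**Reading 3: a separate ANOVA at each visit.** The 2-year test keeps its size (5.0-5.2% in the same simulation), and earlier scores are used at their own visits. Three costs remain.
- *Precision.* Let m be the share missing at 2 years, completely at random. If a model borrows from the 1-year score, its SE relative to attenders only is √(1 − mρ²). At ρ = 0.7, m = 10% gives √0.951 = 0.975, and m = 20% gives √0.902 = 0.950. The attenders-only SE is thus about 2.5% and 5.3% larger than needed. Borrowing from all three earlier visits, the variance ratios are 1.065 and 1.140, so the SE is √1.065 − 1 = 3.2% and √1.140 − 1 = 6.8% larger.
- *Bias.* Assume 10% lost in one arm and 20% in the other, with those lost 0.5-1.0 SD worse at 1 year and a 1-to-2-year correlation of 0.7. If the deficit is measured against the whole arm, the bias is (0.20/0.80 − 0.10/0.90) × 0.7 × (0.5 to 1.0) = 0.049 to 0.097 SD. If it is measured against those who stayed, the bias is (0.20 − 0.10) × 0.7 × (0.5 to 1.0) = 0.035 to 0.07 SD. The SE is √(1/225 + 1/200) = 0.097 SD, so the bias is 0.5-1.0 SE in the first case and 0.36-0.72 SE in the second.
- *Several visits.* With four visits each tested at 5%, the chance of at least one false positive was 18.1%, 15.7% and 13.2% at ρ = 0.3, 0.5 and 0.7.

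**The case against.** The strongest reply is that Section 10 is brief rather than wrong. It neither specifies nor excludes a within-patient term, and no passage says that visits are pooled. The post-hoc wording points to repeated-measures ANOVA as much as to naive pooling. Under the by-visit reading, each test is valid at its own visit and the loss of precision is small. All of this stands.

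A reader might infer three stronger things that the documents do not support:
- *That the trial's error rate will be 15-27%.* This follows only if visits are pooled as independent, which Section 10 does not say.
- *That the plan discards earlier scores.* Under by-visit ANOVA those scores are analysed at their own visits and only fail to inform the visit that was missed. Patients are dropped outright under listwise deletion, and that method does have a within-patient term.
- *That outcome-related loss must bias the 2-year comparison.* With equal loss and an equal deficit in both arms, the formula above gives zero. Bias needs loss that differs between arms, or that relates differently to outcome. The documents give no loss figures, and the intended blinding of patients to group (Section 5) makes a large imbalance less expected.

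The objection does not supply a reading under which the named method handles both correlation and missed visits well. A plan that leaves three readings open also leaves the choice to the analyst.

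**Conclusion.** The point holds as a gap in the stated method for which a better standard method exists. It is not proof of an invalid analysis. Section 10 does not state how four or five scores per patient, or missed visits, enter its ANOVA. Pooling would be invalid, listwise repeated-measures ANOVA would be wasteful, and by-visit ANOVA would be valid in size but would leave known information unused at a missed visit.

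The consequences range from serious (an error rate of about 15-27% if pooled) to modest (an SE about 2.5-5% larger if by visit). The possible bias of roughly 0.035-0.10 SD depends on an assumed 10% versus 20% loss and on how the deficit is defined. Every size given rests on assumed correlations and loss rates, because the documents state none. The change should be made: it settles the choice in advance and is cheap.

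**What to change.** In Section 10, replace the ANOVA and t-tests for the KSS subscales, EQ-5D and FJS by one linear mixed model per score:
- Fixed effects for group, visit and group-by-visit, with an unstructured within-patient covariance.
- All available post-operative scores, including those of patients who later miss a visit.
- Adjustment for the baseline score where it is collected (KSS and EQ-5D; FJS has none).
- The group difference with a 95% confidence interval at each visit.
- A statement that the model assumes data missing at random, and that this covers patients withdrawn after revision under Section 7.3, whose later scores the model in effect extrapolates.

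The cost is a few sentences in Section 10 and slightly more analysis work. No new data are needed, and SPSS can fit such models. The downside is reliance on the missing-at-random assumption, which may be hard to defend for revised patients. The model also does not settle which score and visit are primary, so the several-visits problem stays open until the plan names them.

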3. OBJECTIVES

The objectives of the study are twofold: 1) Evaluate how intra-operative sensing may assist the surgeon with tibiofemoral rotational alignment by testing the precision and variability of setting tray rotation to the mid-third of the tibial tubercle. 2) Understand if patients with a combined axial rotation couple at the tibiofemoral joint and quantitative intercompartmental balance, achieved with the use of VERASENSE, exhibit less post-operative knee pain and improved clinical outcomes. Radiographic outcomes will also be assessed to measure post-operative alignment and to evaluate the prevalence and location of radiolucency and/or osteolysis.

Hypothesis: TKA with VERASENSE results in a more reliable and precise option for establishing implant-to-implant congruency and joint balance leading to less knee pain, faster return to normal activities and higher patient satisfaction compared to TKA without VERASENSE.

The secondary objectives of the study are to establish correlations between the intraoperative VERASENSE data, the surgeon's perception of balance and patient outcomes in addition to understanding any learning curve associated with using new technology.

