5. METHODS / PROCEDURES

Patients indicated for TKA and who meet all study eligibility criteria will be asked to participate in the study. Eligible patients will receive a primary unilateral PCL-retaining or – sacrificing TKA using the Stryker Triathlon Total Knee System *with* or *without* the use of the VERASENSE™ Knee System. Patients will be enrolled in a consecutive series consisting of two cohorts (Groups A and B). Both groups are described below:

Group A – Control (Surgeon-Guided) will consist of **250** consecutive patients who will undergo primary unilateral PCL-retaining or – sacrificing TKA using the Stryker Triathlon Total Knee System *without* the use of VERASENSE to guide rotational alignment and balance. **Prior to closing the arthrotomy, VERASENSE will be utilized in a surgeon-blinded fashion to record rotational alignment and intercompartmental pressures through a range of motion.**

Group B (Sensor-Guided) will consist of **250** consecutive patients who will undergo primary unilateral PCL-retaining or – sacrificing TKA using the Stryker Triathlon Total Knee System *with* the use of VERASENSE to guide rotational alignment and balance. The sensor data will be used for balancing per the VERASENSE protocol below.

Each patient will be given a unique study number once informed consent has been obtained. The investigator will be blinded to the patient study number and the patient will be blinded to his/her assigned group. It will be important that all patients remain blinded to their assigned group. The patient will be informed during the consent process that they may or may not receive their knee replacement procedure using the VERASENSE Knee System.

Radiographic outcomes will be assessed on all patients within the first 12 weeks and at the annual visits. Any postop complications will also be monitored.

Surgical Protocol – Using VERASENSE

All knees will be prepared using standard instrumentation and a measured resection or gap balancing technique. The following steps will be performed when using VERASENSE:

Step 1: Establish Tibial Tray Rotation:

Select and position appropriate sized trial tibial tray. Align the tray to the anatomy (mid-medial third of the tubercle) as recommended by the manufacturer's surgical technique. Insert a single anterior or posterior pin (medially or laterally) into the trial tray to allow for internal / external rotational adjustment while maintaining optimal medial / lateral coverage.

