Figure 2 - view of proximal tibia referencing the mid-medial third of tibial tubercle

Step 2: Sensor Insertion

Insert the VERASENSE Sensor with appropriate sized shim attached to replicate thickness of standard trial insert. In a tight knee capsule, it may be necessary to insert the VERASENSE Sensor prior to insertion of the femoral trial. DO NOT utilize excessive force or impact the sensor directly with a mallet.

Figure 3 - VERASENSE™ Sensor activated and inserted into knee

Step 3: Establish Tibial Tray Rotation Utilizing Contact Points

With the leg supported in 10° flexion, rotate the tibial tray to the most posterior contact point (internally or externally) as needed to horizontally align the medial and lateral contact points within 5° of each other. Reference protocol found in Appendix I on how to hold the leg using VERASENSE. A positive (+) value in the Contact Point Rotation (CP Rotation box) indicates internal rotation (IR); a negative (-) value indicates external rotation (ER). Figures 4-6.

When preferred tray rotation is achieved (within 5° Contact Point Rotation):

- Add additional Pin to stabilize tray
- Flex knee and confirm patellar tracking
- Record the final value

[figure not shown]

Figure 4 - VERASENSE™ Sensor as displayed on graphical user interface. CP (Contact Point) Rotation degree [in red box] references the degree of tibiofemoral incongruity. Yellow circles correspond to femoral contact points. The number 8 represents total pounds of pressure in the medial and lateral compartments

Figure 5 - Left: Medial and lateral femoral contact points (indicated by arrows) demonstrate tibiofemoral rotational incongruity, due to excessive IR of the tibial tray. Right: After correcting for IR, the femoral contact points demonstrate symmetry (indicated by arrows).

Figure 6 - Left: Example of excessive ER (indicated by arrows), as a result of referencing the mid-third of the tibial tubercle, shown by the sensor interface. Middle: Trial tibial/femoral components in place with the sensor; tibial tray visually and digitally exhibiting external rotation. Right: The tibial tray is rotated to improve congruity, as seen by the parallel contact points (indicated by arrows) on the sensor interface.

Step 4: Balance Soft-Tissue Sleeve

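### Section 10 tests every outcome for significance but names no primary outcome, visit, alpha or error rule, and gives no measure of variability for the precision objective

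*Combined protocol and SAP*

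**What the plan says.** Section 10 is the only analysis text in the document. It applies comparative statistics to outcomes data that it does not itemise: "Analysis of variance (AVOVA) will be used to assess the difference between each group, with post-hoc t-tests to demonstrate significance". It adds: "Separate analyses will be performed to evaluate power of sample sizes and any correlative affect that demographic/clinical variables may have on patient outcomes". No significance level, primary outcome, primary visit, effect size, power or multiplicity procedure appears here or elsewhere.

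Section 3 gives two main objectives without ranking them. The first is about "testing the precision and variability of setting tray rotation to the mid-third of the tibial tubercle". The second concerns pain and clinical outcome. The hypothesis joins several claims: "TKA with VERASENSE results in a more reliable and precise option for establishing implant-to-implant congruency and joint balance leading to less knee pain", followed by return to activity and satisfaction. Secondary objectives are listed, but neither main objective is tied to an endpoint.

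Rotation is recorded in both groups (Section 5). In Group A, before the joint is closed, "VERASENSE will be utilized in a surgeon-blinded fashion to record rotational alignment and intercompartmental pressures through a range of motion". In Group B, Step 3 has the final value recorded "When preferred tray rotation is achieved (within 5° Contact Point Rotation"), with the leg at 10° of flexion and before the soft-tissue balancing of Step 4.

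Table 1 collects EQ-5D and KSS before surgery and at four later visits. FJS is collected at the four later visits and the knee pain form at three, both without a baseline. The opening sentence of Section 9c reads "Data will be collected pre-operatively, intra-operatively, and post-operatively at 6 weeks, 6 months, and 1 year". Section 2 says "Clinical Assessments will be performed at baseline, 6 weeks, 6 months, 1 and 2 years after surgery", and the visit windows and Table 1 also include year 2.

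**The concern.** The plan relies on significance without saying which result counts or at what level. Several instruments are measured at several visits, so a chance finding somewhere is likely, and a reader of the final report could not tell a planned result from a selected one.

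The first main objective could also end without a test that answers it. Two groups can have the same mean rotation and very different scatter, and a comparison of means would miss that.

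The lesser matter is that baseline KSS and EQ-5D are collected, but no place is stated for them in the group comparison. Demographic and clinical variables appear only in separate analyses, and centre is not mentioned.

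**Working it through.** **The plan's own figure.** The sample size cannot be reproduced, because the document gives no alpha, power, effect or SD. Only the counts check: 250 + 250 = 500, and 500/100 per centre implies about five centres.

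**Does the post-hoc step protect?** At one visit with two groups, F = t² and the p-values are identical. A t-test that follows a significant ANOVA is the same test again.

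**How many tests?** From Table 1, after surgery:
- One test per outcome: EQ-5D, KSS, FJS, pain form = 4.
- Every visit: 4 + 4 + 4 + 3 = 15.
- Every visit, without year 2: 3 + 3 + 3 + 2 = 11.
- Every visit, with KSS split into its four parts (objective score, satisfaction, function, expectations): 4 + 16 + 4 + 3 = 27.

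Radiographs and intra-operative readings are left out. Section 5 and Table 1 give different radiograph schedules, and a true difference in the intra-operative readings is expected because the sensor steers them.

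**Chance of any false positive.** Assumptions (none is in the document): two-sided 5% per test, all nulls true, common correlation ρ between test statistics. For ρ = 0 the chance is 1 − 0.95^m, so m = 4 gives 0.185 and m = 15 gives 0.537. For ρ > 0 it is 1 − ∫[Φ((1.96 − √ρ·u)/√(1−ρ)) − Φ((−1.96 − √ρ·u)/√(1−ρ))]^m φ(u) du.

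| Tests m | ρ = 0 | 0.3 | 0.5 | 0.7 | 0.9 |
|---|---|---|---|---|---|
| 4 | 18.5% | 17.4% | 15.6% | 13.0% | 9.4% |
| 11 | 43.1% | 37.5% | 30.4% | 22.3% | 13.1% |
| 15 | 53.7% | 45.7% | 36.1% | 25.6% | 14.4% |
| 27 | 75.0% | 63.0% | 48.3% | 32.6% | 17% |

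With correlation 0.5 to 0.7 within an outcome and 0.3 to 0.5 between outcomes, simulation gives about 33% to 43% for 15 tests.

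The mildest reading is a gated one: a visit-level t-test counts only if that outcome's overall group effect is also significant. For four outcomes at four visits (correlation 0.5 to 0.7 within, 0 to 0.5 between), simulation gives 13.7% to 18.3%.

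**Can a comparison of means answer a precision question?** With 250 per group, equal means and SD ratios from 1.0 down to 0.5, the simulated t-test rejected about 4% to 6% of the time. That is its nominal rate, whatever the difference in spread. With normal data and an SD ratio of 1.20, the Brown-Forsythe test had about 76% power at the 5% level and 53% at 1%.

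**What does a baseline term buy?** The effect of 0.25 SD is my choice, because the document states none. Power comes from the noncentral t with noncentrality 0.25·√(n/2)/√(1−r²), where r is the assumed correlation of baseline with outcome. For n = 250 per group at 5%:
- Unadjusted: noncentrality 2.795, power 80%.
- r = 0.3: 2.795/√0.91 = 2.930, power 83%.
- r = 0.5: 2.795/√0.75 = 3.227, power 90%.

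At a 4% level, power is 77%, 79%, 81% and 88% for r = 0.1, 0.2, 0.3 and 0.5. With an assumed 15% loss (250 × 0.85 ≈ 212 per group), the 4% test has 74% at r = 0.3 and 82% at r = 0.5.

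**The case against.** **The error rates are assumed, and the largest are unrealistic.** This stands in part. Visits on the same patients are correlated, so the figures at ρ = 0 are upper bounds. A reader might take 54% or 75% as this trial's actual error rate; the document gives neither an alpha nor a correlation to support that. The direction does not depend on the choice, since even at 0.9 the figures are 9% and 14%.

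**ANOVA can test spread.** This stands. Brown-Forsythe is itself an ANOVA, on absolute deviations, so it would go too far to say that the named method could never serve objective 1. The supportable statement is that no measure of variability is specified.

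**The recorded rotation values may not answer objective 1.** This also stands, and it limits the remedy. Group B's required value comes before balancing, and Group A's comes just before closure, through a range of motion. In Group B the tray may have been rotated away from the tubercle landmark that the objective names, using the same reading that would be the outcome. It would be tempting to infer that the existing readings already allow a test of precision to the landmark, but Section 5 does not support that.

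**Section 10 lists no model terms, so baseline is not excluded.** This is fair. Silence does not show that the analysis will omit baseline. Nor does an unadjusted comparison become biased in a randomised trial; it is valid and less efficient.

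**Conclusion.** The concern holds. Under every reading checked, following Section 10 as written gives a chance of a false positive above 5%: about 19% to 13% with one test per outcome, and 54% to 26% with every visit tested (correlation 0 to 0.7). This assumes 5% two-sided tests and no true effects. Objective 1 has no specified measure of variability, and comparing mean rotation would not answer it.

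The must-fix rating rests on the missing primary outcome, visit and error rule. The baseline and centre terms alone would be a should-fix: a free gain, with no threat to validity.

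Two further inferences are not supported. The document does not claim 80% power, so that figure is no benchmark the plan has set itself. Nor can error control be called costless: a 4% clinical test with baseline matches an unadjusted 5% test only if the baseline correlation is above about 0.26. Finally, nothing in the document shows that results have been selected; the point is that the plan would not prevent it.

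**What to change.** Amend Section 10, with a date, before anyone at the sponsor reviews outcomes by group. The document does not show the trial's status, so the amendment should state it.

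1. Name one primary clinical outcome and one visit, with a two-sided 5% level. The choice is the sponsor's.
2. For objective 1, name one rotation measure. Compare its spread (Brown-Forsythe) or the proportion within the protocol's own 5° target, using readings from the same stage and flexion angle in both groups. First confirm that a comparable Group B reading is recorded; if not, report the comparison as descriptive. State that Group B is steered by the same reading and may have left the tubercle landmark, so the result shows that sensor congruency was reached, not precision to the landmark.
3. Control 5% across the two objectives by a fixed order or a split. If objective 1 is descriptive, it needs no share.
4. Test other outcomes and visits as confirmatory (stated order or Holm) only after the primary tests succeed and within the same overall 5%. Label the rest exploratory.
5. Analyse KSS components and EQ-5D by ANCOVA at the chosen visit, or by a repeated-measures mixed model with group, visit and group-by-visit. Include centre, and the baseline score where the pre-operative KSS version has a matching component. Use the same model without baseline for FJS, and logistic regression with centre for knee-pain prevalence. Drop the post-hoc t-tests.
6. Reconcile the opening sentence of Section 9c with the 2-year visit, so that the set of tests is fixed.

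**Cost.** This is text only, with no new patients. Under Section 16 it needs sponsor and investigator approval and the relevant IRBs, at about five centres. Isolated secondary p-values can no longer be claimed as proof. A fixed order blocks the second objective if the first fails. A 4%/1% split gives the clinical test 77% to 88% power at 0.25 SD (baseline correlation 0.1 to 0.5), or 74% to 82% with 15% loss (0.3 to 0.5). It lowers power for objective 1 from 76% to 53% at an SD ratio of 1.20.
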